### **Identification of candidate prognostic factors**

When developing a prognostic model, selection of candidate prognostic factors should be guided by evidence from the literature and consultations with content experts [37]. The included studies collected candidate predictors based on existing literature and expert knowledge using sociodemographic and clinical variables. The predictor data from the cohort and the MI-NAV study are nearly identical, but differ slightly from the MI study. For model development, we identified those prognostic factors that are available in all three datasets. Since the aim of our prognostic models is to predict

prolonged sickness absence with as good accuracy as possible, we included both modifiable and non-modifiable prognostic factors.

We identified a set of prognostic factors for the model development based on an iterative approach:

- 1. We identified candidate predictors of sickness absence from available literature:** The first author (TR) reviewed all available best-evidence synthesis of systematic reviews [28], systematic reviews [38–43], prognostic model studies [10–15,17,18,35,44–51], and expert opinions from Delphi-studies [52,53]. Additional focused searches on PubMed (<https://pubmed.ncbi.nlm.nih.gov>) for relevant prognosis studies were also conducted to identify additional evidence for candidate prognostic factors.
- 2. Clinical grounds through discussion in a multidisciplinary group:** The candidate prognostic factors from the literature review were shared with the research group, and through discussion we selected a set of prognostic factors to be used for model development, restricted to data availability and sample size calculation (see “Sample size” section).

The prognostic factors that were identified and that will be included in the model are summarised in Table 2. Because we will use data from randomised controlled trials, we must consider the extraneous trial effects which can limit the generalisability of the model validation [54]. Thus, we will model for treatment effect by following the guidance provided by Pajouheshnia et al. [54]. We will code the intervention predictor as a binary variable, to avoid overcomplicating the model.

**Table 2.** Summary of selected prognostic factors for model development with definition, variable type, unit/categories, measurement method, number of predictor parameters, and evidence.

Prognostic factor	Definition	Variable type	Unit/categories	Measurement method	No. of predictor parameters	Evidence
Expectation of RTW	Expectation of probability of returning to work within 3 months	Continuous	0-10, 10 = best	Self-reported using item from ÖMPSQ-SF [55]	1	[14,17,28,40,52,56–63]
Pain intensity	Pain intensity last week	Continuous	0-10, 10 = worst	Self-reported	1	[17,38,43,52,53,61–65]

Depression/ anxiety	Self-reported depression or anxiety	Categorical	Recategorized from 5 to 3 categories	Self-reported using item from EQ5D [66]	3	[10,28,43,67]
Education level	Completed education	Binary	0 'Lower education: primary/secondary/voc ational school' 1 'Higher education: College/University. Recategorized from 4 to 2 categories	Self-reported	1	[10,13,14,18,2 8,44,45,52,53, 59]
Age	Age	Continuous	Years	Self-reported	1	[4,10,14,17,18 ,28,38–40,43– 46,52,53,56,5 8–63]
Previous sick leave	Days of sick leave previous year	Continuous	Days	Register data	1	[4,10,17,18,28 ,45,46,52,53,5 6]
Disability pension status	Receiving work assessment allowance or disability pension at starting-point	Binary	0 'No' 1 'Yes'	Register data	1	[4,10,17,18,28 ,45,46,52,53,5 6]
General health	Self-perceived general health	Continuous	0-100	Self-reported using VAS from EQ5D [66]	1	[10,18,40,44,4 5,52,53,61,62]
Fear- avoidance	Fear that movement or activity will worsen the injury	Binary	0 'No' 1 'Yes'	Self-reported using item from Keele STarT MSK tool [68,69]	1	[39,40,43,53]
Workability (job performance)	Self-reported current workability compared to at its best	Continuous	0-10, 10=best	Self-reported using item from Work Ability Index [35]	1	[18,35,44,46,5 2,53]
Intervention	Participant in a trial arm with an effective intervention	Binary	0 'No' 1 'Yes'		1	[70]
					Total 13	

[figure not shown]
Abbreviations: EQ5D, Euroqol questionnaire 5-dimensions; ÖMPSQ-SF, Örebro Musculoskeletal Pain Screening Questionnaire short form; RTW, return to work; SA, sickness absence; VAS, visual analogue scale.

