### Development

The sample size is fixed at 934 participants in the development sample. To adequately power the regression analysis and potential exploratory analysis, we will follow recent sample size recommendations by Riley et al. [71,72] using the *pmsampsize* module in STATA 16.1 (StataCorp LLC, Texas, USA). This prediction sample size calculator is also available online: <https://riskcalc.org/pmsamplesize/>.

In order to include all prognostic factors, corresponding to Table 1 and including 2 parameters for each continuous predictor to account for potential non-linear trends, 19 parameters ( $P$ ) are needed. We will target an expected shrinkage factor ( $S$ ) of 0.9, to

reflect small optimism in predictor effect estimates, as recommended by Riley et al. [72]. We assume that the models will have a modest Nagelkerke's  $R^2$  of 25% which corresponds to a Cox-Snell  $R^2$  of 0.185.

- For the first end-point (>90 days), the event rate is 0.403 (416 events of 934), which gives a minimum required sample size ( $n$ ) of 826 (with 368 events), resulting in an event per predictor parameter (EPP) of 19.35.
- For the second end-point (>180 days), the event rate is 0.172 (161 events of 934), which results in a minimum required sample size ( $n$ ) of 826 (with 143 events) and an EPP of 7.48.
- For the third end-point (WAA/DP), the event rate is 0.108 (101 events of 934), which gives a minimum required sample size ( $n$ ) of 826 (with 90 events) and an EPP of 4.7.

Our fixed sample size exceeds these minimum requirements. Therefore, we expect our study to be adequately powered which will lead to minimal shrinkage and reliable results.

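### Table 2 charges three parameters to the three-category depression/anxiety factor; with two, the totals become 12 and 18 and the minimum development sample becomes 783, not 826

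*SAP*

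**What the plan says.** In the SAP, Table 2 (Identification of candidate prognostic factors) gives each predictor a number of parameters. Depression/anxiety is categorical, with the note "Recategorized from 5 to 3 categories", and the row ends "Self-reported using item from EQ5D [66] 3", the last figure being the parameter count. Education, reduced to two categories, is counted as 1. So are the three other binary factors: disability pension status, fear-avoidance and intervention. Each of the six continuous predictors is also counted as 1, and the printed total is 13.

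The Development part of the Sample size section then doubles the continuous predictors: "including 2 parameters for each continuous predictor to account for potential non-linear trends, 19 parameters". (That text points to Table 1, but the predictors are in Table 2.) From P = 19 it derives a minimum of 826 participants for each end-point, with 368, 143 and 90 events and 19.35, 7.48 and 4.7 events per predictor parameter (EPP). It concludes that the fixed 934 participants exceed this.

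**The concern.** The models are multivariable logistic regressions, and the Model performance section plans to re-estimate the intercept after shrinkage, so the model has one. A three-level factor then has a reference level and two coefficients; a third indicator would be collinear with the intercept. Table 2 follows levels minus one for every two-level factor but counts all the levels of its only three-level factor.

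The count serves as a budget. The SAP says that predictor selection was restricted by the sample-size calculation, and its Exploratory prognostic factors section makes the scope of the exploratory work depend on that calculation and on the number of parameters in the full model. A wrong P misstates the minimum sample, the required events and the room left for exploratory predictors.

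**Working it through.** **Parameter count, from Table 2**

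- Continuous (6): expectation of return to work, pain intensity, age, previous sick leave, general health, workability.
- Binary (4): education, disability pension status, fear-avoidance, intervention.
- Three-level (1): depression/anxiety.

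| | Depression/anxiety = 3 (as printed) | Depression/anxiety = 2 |
|---|---|---|
| Table 2 total | 6 + 4 + 3 = 13 | 6 + 4 + 2 = 12 |
| P with continuous predictors doubled | 12 + 4 + 3 = 19 | 12 + 4 + 2 = 18 |

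Both printed totals, 13 and 19, need the 3, so it is not an isolated misprint in one cell.

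**Inputs, from Sample size, Development**

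- Target: "expected shrinkage factor ( $S$ ) of 0.9".
- Nagelkerke R² "of 25% which corresponds to a Cox-Snell" R² of 0.185, used for all three end-points.
- Events among 934: 416, 161 and 101, so the rates are 416/934 = 0.445, 161/934 = 0.172 and 101/934 = 0.108. For end-point 1 the SAP prints "the event rate is 0.403 (416 events of 934". Its 368 events and EPP of 19.35 reproduce only with 0.445, so 0.445 is used here.

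**Reproducing the SAP's figure.** The SAP names the sample-size command but does not print the formula. The shrinkage criterion of that method is

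n = P / [(S − 1) ln(1 − R²/S)].

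Here ln(1 − 0.185/0.9) = ln(0.7944) = −0.2301, so the denominator is 0.02301. With P = 19, n = 825.7, rounded up to 826. This is the SAP's figure.

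The method's other two criteria were also checked, with margins of 0.05 (an assumption, as the SAP states none). At P = 19 they give 450, 562 and 683 (optimism in R²) and 380, 220 and 149 (precision of overall risk). None exceeds 826, so the shrinkage criterion decides. At P = 18 they give at most 427, 532 and 647, and it still decides.

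**With P = 18.** n = 18/0.02301 = 782.2, rounded up to 783. That is 43 fewer, or 43/826 = 5.2%.

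| End-point | Events at n = 826 (SAP) | Events at n = 783 | EPP printed | EPP at n = 783, P = 18 |
|---|---|---|---|---|
| >90 days | 368 | 348.7, about 349 | 19.35 | 19.37 |
| >180 days | 143 | 135.0, about 135 | 7.48 | 7.50 |
| WAA/DP | 90 | 84.7, about 85 | 4.7 | 4.70 |

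**Why EPP does not move.** EPP at the minimum sample is n × rate / P. Since n is proportional to P, this equals rate / [(S − 1) ln(1 − R²/S)], which does not contain P. The small differences come from rounding n and the rates.

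**Parameters supported by 934.** 934 × 0.02301 = 21.49, so 21 parameters fit at S = 0.9. That leaves 21 − 19 = 2 spare on the printed count and 21 − 18 = 3 on the corrected count. Expected shrinkage at n = 934 is 0.910 with P = 19 and 0.915 with P = 18.

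**The case against.** The strongest reply is that nothing in the analysis changes. The sample is fixed, the full-model approach keeps every predictor, and software will fit two indicators whatever the table says. The error overstates the requirement, and 934 exceeds both 826 and 783. All of this stands, and it limits the point to a correction of stated figures.

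A second reply is that the 3 may be deliberate. Four categories would use three parameters, in which case the category note would be the error and 13 and 19 would stand. A separate level for missing answers would also use a third, but the Missing data section plans complete-case analysis or multiple imputation, not a missing category. The SAP gives no reason for a third parameter, so either the count or the category note needs correcting.

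A reader might also infer that the printed EPPs are wrong by the ratio 19/18. They are not, because P cancels. EPP taken at n = 934 would rise from 21.9, 8.5 and 5.3 to 23.1, 8.9 and 5.6, but the SAP does not report EPP on that basis. Nor did the miscount rule out a finer category: on the SAP's inputs 934 already supports 21 parameters.

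**Conclusion.** The parameter totals, minimum sample size and required events are wrong as written. They should be 12 and 18 parameters, 783 participants and about 349, 135 and 85 events. The EPPs stand. The point is minor and conservative, and it does not by itself change the SAP's conclusion that 934 exceeds the minimum. Its practical effect is one more spare parameter (3 rather than 2) for the exploratory work.

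This rests on three categories being intended, on a model with an intercept, and on the SAP's shrinkage target and its single Cox-Snell value of 0.185. Whether that one value suits all three end-points is a separate question that arises equally with 18 or 19 parameters. The spare count should be read only on the SAP's own input, and nothing here shows that 934 is too few because of the miscount.

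**What to change.** In Table 2 set depression/anxiety to 2 parameters and the total to 12. In Sample size, Development, set P to 18, re-run the command, and restate the minimum sample (783 on the present inputs) and the required events for each end-point. Point the text to Table 2. Then restate how many parameters remain for the exploratory analysis. If a third parameter is intended, say what it represents, correct the category note if needed, and keep 13 and 19. The cost is a few words in the SAP and one re-run; no data or analysis code is affected.

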## Exploratory prognostic factors

The review and discussion process also resulted in a list of exploratory prognostic factors, that are less well-established in the literature but are considered to be important factors for sickness absence. These prognostic factors will be investigated to see if the model performance improves by adding one or more of these exploratory factors to the model. The scope of this exploratory analysis depends on the sample size calculation and the number of predictor parameters of the full model (see 'Sample size' section). Therefore, this will be investigated outside the planned principal analysis.

## Sample size

The flow of study participants for both the development sample and the validation sample is presented in Figure 1.

**Figure 1.** Flow of participants through study.

### Development

The sample size is fixed at 934 participants in the development sample. To adequately power the regression analysis and potential exploratory analysis, we will follow recent sample size recommendations by Riley et al. [71,72] using the *pmsampsize* module in STATA 16.1 (StataCorp LLC, Texas, USA). This prediction sample size calculator is also available online: <https://riskcalc.org/pmsamplesize/>.

In order to include all prognostic factors, corresponding to Table 1 and including 2 parameters for each continuous predictor to account for potential non-linear trends, 19 parameters ( $P$ ) are needed. We will target an expected shrinkage factor ( $S$ ) of 0.9, to

reflect small optimism in predictor effect estimates, as recommended by Riley et al. [72]. We assume that the models will have a modest Nagelkerke's  $R^2$  of 25% which corresponds to a Cox-Snell  $R^2$  of 0.185.

- For the first end-point (>90 days), the event rate is 0.403 (416 events of 934), which gives a minimum required sample size ( $n$ ) of 826 (with 368 events), resulting in an event per predictor parameter (EPP) of 19.35.
- For the second end-point (>180 days), the event rate is 0.172 (161 events of 934), which results in a minimum required sample size ( $n$ ) of 826 (with 143 events) and an EPP of 7.48.
- For the third end-point (WAA/DP), the event rate is 0.108 (101 events of 934), which gives a minimum required sample size ( $n$ ) of 826 (with 90 events) and an EPP of 4.7.

Our fixed sample size exceeds these minimum requirements. Therefore, we expect our study to be adequately powered which will lead to minimal shrinkage and reliable results.

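### SAP, Sample size (Development): the end-point 1 event rate is printed as 0.403, but its own count, 416 of 934, is 0.445; one rate should be verified and carried through the calculation

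*SAP*

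**What the plan says.** The Development part of the SAP's Sample size section sets out one calculation for three models, using the pmsampsize module. Its common inputs come first:

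- Sample: "The sample size is fixed at 934 participants in the development sample".
- Parameters: "19 parameters ( $P$ ) are needed".
- Shrinkage: "We will target an expected shrinkage factor ( $S$ ) of 0.9".
- Explained variation: a Nagelkerke R² "of 25% which corresponds to a Cox-Snell" R² of 0.185. This is stated once, ahead of the three end-points, and no event rate is attached to it.

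For end-point 1 it then says that "the event rate is 0.403 (416 events of 934", and gives a minimum sample size "of 826 (with 368 events", "resulting in an event per predictor parameter (EPP) of 19.35". The section concludes that the fixed sample exceeds the minimum.

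**The concern.** A proportion and the count it is said to come from stand in the same bracket and do not agree. The gap is about 40 events in 934, too large for rounding. The corresponding brackets for the other two end-points are consistent (161/934 = 0.172 and 101/934 = 0.108), so it is clear how the rate was meant to be formed, and only end-point 1 departs from it.

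The event rate is an input to the method. It fixes the maximum attainable Cox-Snell R², and so the Cox-Snell value that matches a given Nagelkerke value. It also turns the minimum sample size into events and EPP. If the two steps used different rates, the printed line cannot be rebuilt from its own stated inputs. At stake is whether the justification for the first-listed and most frequent outcome can be reproduced, and whether its baseline risk is correctly described.

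**Working it through.** **Inputs**, all from the SAP, Sample size, Development: N = 934; P = 19 parameters; target shrinkage S = 0.9; Nagelkerke R² = 0.25; Cox-Snell R² = 0.185; rate φ = 0.403 or 416/934. The SAP prints no formulas. The standard ones for a binary outcome are used below; they reproduce the SAP's 826.

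**Step 1: the bracket.**
- 416/934 = 0.4454.
- 0.403 × 934 = 376.4, so about 376 events.

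**Step 2: the plan's minimum n.** The shrinkage criterion is n = P / [(S − 1) ln(1 − R²/S)].
- With R² = 0.185: 19 / [(−0.1) × ln(1 − 0.185/0.9)] = 825.7, rounded up to **826**. This is the printed figure.
- The criterion for optimism in R² (0.05) gives about 450, and the criterion for precision of the overall risk (margin 0.05) gives about 370 to 380. The shrinkage criterion therefore determines n.

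**Step 3: the plan's events and EPP.** Events = n × φ; EPP = events / P.

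| φ | Events at n = 826 | EPP |
|---|---|---|
| 0.445 | 826 × 0.445 = 367.6, i.e. 368 | 367.6/19 = 19.35 |
| 0.403 | 826 × 0.403 = 332.9, i.e. 333 | 332.9/19 = 17.5 |

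The printed 368 and 19.35 follow 0.445, not the printed 0.403.

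**Step 4: the R² conversion.** Maximum Cox-Snell R² = 1 − exp{2[φ ln φ + (1 − φ) ln(1 − φ)]}, and Cox-Snell R² = 0.25 × that maximum.
- φ = 0.403: maximum 0.7403, Cox-Snell 0.1851.
- φ = 416/934: maximum 0.7470, Cox-Snell 0.1867.
- Only rates from about 0.393 to 0.411 give a value that rounds to 0.185.
- Read in reverse at φ = 416/934: 0.185/0.7470 = 24.8% Nagelkerke.

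**Step 5: one rate throughout, R² unrounded.**

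| Quantity | Printed | φ = 416/934 | φ = 0.403 |
|---|---|---|---|
| Events in 934 | 416 | 416 | 376 |
| Cox-Snell R² | 0.185 | 0.1867 | 0.1851 |
| Minimum n | 826 | 816.99, i.e. 817 | 825.2, i.e. 826 |
| Events at minimum n | 368 | 363.9, i.e. 364 | 333 |
| EPP | 19.35 | 19.15 | 17.5 |

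Neither column returns the whole printed set when the conversion from 25% Nagelkerke is included. Solving the Step 2 formula for S at n = 934 gives an expected shrinkage factor of 0.911 at 416/934 and 0.910 at 0.403, both above the 0.9 target.

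**The case against.** The strongest reply is that 0.403 is a stale or misprinted figure and nothing more. Three printed numbers (416, 368 and 19.35) agree with 0.445, and once Cox-Snell R² is fixed at 0.185 the binding formula contains no event rate. A single run with R² = 0.185 and prevalence 0.445 returns 826, 368 and 19.35. That is correct. A reader might infer that the printed results cannot have come from one run, and the documents do not support that. Any mismatch lies before the run, in the conversion from Nagelkerke to Cox-Snell.

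Even there the evidence is indirect. The SAP does not say which rate produced 0.185, and 24.8% would round to the stated 25%. The closer fit to 0.403 is worth reporting because 0.403 is also the printed rate, but it remains an inference.

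A reader might also divide 416 by 0.403, obtain about 1,032, and suspect a different analysis set. That number matches neither 934 nor the two source studies combined (549 + 514 = 1,063), and nothing in the SAP points to such a set.

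Finally, nothing downstream turns on the discrepancy: the SAP compares EPP with no threshold, and 934 is enough at either rate. This limits the weight of the point but does not remove the contradiction in the bracket.

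**Conclusion.** The printed end-point 1 rate and count contradict each other, and one of them is wrong. On the internal evidence the count is better supported, since the events and EPP follow it. However, the R² conversion leans towards 0.403, so the documents alone do not settle which entry is in error.

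The size is small. Depending on the rate, minimum n moves between 817 and 826, the events at that n between 364 and 333, and EPP between about 19.2 and 17.5. The end-point 1 conclusion that 934 exceeds the minimum holds in both cases, and it would be wrong to read this as a sample-size shortfall for that model. The result rests on the SAP's own P = 19, S = 0.9 and 25% Nagelkerke, and on the standard criteria that reproduce its 826. It says nothing about the adequacy of the sample for end-points 2 and 3, to which the same 0.185 is applied; that is a separate question.

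**What to change.** Verify the end-point 1 count in the 934 development participants, print one event rate, and recompute Cox-Snell R², minimum n, events and EPP from it.

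- If 416 stands: rate 0.445, R² 0.1867, minimum n about 817, about 364 events, EPP about 19.2.
- If 0.403 stands: 376 events in 934, R² 0.185, minimum n 826, 333 events, EPP 17.5.

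Carry R² unrounded and state the rate used for the conversion. Rounding matters at the last digit: R² entered as 0.187 gives 815.75, hence 816, not 817.

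The cost is a recount and one corrected line in the SAP. No analysis, outcome definition or end-point 1 conclusion has to change.

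### One Cox-Snell R² is used for three different event rates, so 934 participants fall short of the plan's own minimum for the >180-day and WAA/DP models

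*SAP*

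**What the plan says.** All of this stands in the SAP under Sample size, Development. The sample is given: "The sample size is fixed at 934 participants in the development sample". The authors use the published sample-size criteria for prediction models, through the pmsampsize module, with a target shrinkage factor of 0.9. On model size they write: "including 2 parameters for each continuous predictor to account for potential non-linear trends, 19 parameters ( $P$ ) are needed". One Nagelkerke R² of 25% is assumed for the models and equated with one Cox-Snell R² of 0.185.

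Three calculations follow:

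- **End-point 1 (>90 days):** "the event rate is 0.403 (416 events of 934), which gives a minimum required sample size" of 826, with 368 events and 19.35 events per parameter.
- **End-point 2 (>180 days):** "the event rate is 0.172 (161 events of 934), which results in a minimum required sample size" of 826, with 143 events and 7.48 per parameter.
- **End-point 3 (new or increased WAA/DP):** "the event rate is 0.108 (101 events of 934), which gives a minimum required sample size" of 826, with 90 events and 4.7 per parameter.

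The section closes with "Our fixed sample size exceeds these minimum requirements" and infers that little shrinkage is to be expected.

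**The concern.** The same minimum appears for event rates of about 0.40, 0.17 and 0.11. If the assumption is a fixed Nagelkerke R², this cannot be right. Nagelkerke's measure is Cox-Snell R² divided by its maximum, and that maximum depends on the event rate. A fixed Nagelkerke value therefore means a smaller Cox-Snell value for a rarer outcome, and a smaller Cox-Snell value means a larger required sample.

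The adequacy of the WAA/DP and >180-day models is at stake. The calculation also bears on model content. The section on identification of candidate prognostic factors says selection was limited by the sample-size calculation, and the section on exploratory factors makes the scope for further predictors depend on it. The allowance of a second parameter for each continuous predictor looks affordable only if 826 is correct.

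End-point 1 has an additional mismatch: its printed event rate does not agree with its printed event count.

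**Working it through.** **Inputs.** From Sample size, Development: n = 934; target shrinkage S = 0.9; Nagelkerke R² = 0.25; events 416, 161 and 101. P = 19 agrees with Table 2: 13 parameters, plus one more for each of the six continuous predictors.

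**Formulas.**

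- Maximum Cox-Snell R²: max = 1 − exp{2[p ln p + (1−p) ln(1−p)]}
- Cox-Snell R² = Nagelkerke R² × max
- Shrinkage criterion: n = P / [(S − 1) ln(1 − R²/S)], with R² the Cox-Snell value

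**Reproducing the plan's figure.** With R² = 0.185, ln(1 − 0.185/0.9) = −0.2301, so n = 19 / (0.1 × 0.2301) = 825.7, rounded up to 826. The event rate does not enter this formula except through R², which is why holding R² at 0.185 returns 826 three times.

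**Where 0.185 comes from.** At p = 0.403, max = 0.740 and 0.25 × 0.740 = 0.185. The SAP does not state the rate used for the conversion, but this one fits. At the other two rates, 0.185 implies a Nagelkerke R² of 0.185/0.601 = 30.8% and 0.185/0.496 = 37.3%, not 25%.

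**Converting at each end-point's own rate** (exact counts, unrounded R²):

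| | >90 days | >180 days | WAA/DP |
|---|---|---|---|
| p | 416/934 = 0.4454 | 161/934 = 0.1724 | 101/934 = 0.1081 |
| max | 0.747 | 0.601 | 0.496 |
| Cox-Snell R² | 0.1867 | 0.1503 | 0.1240 |
| ln(1 − R²/0.9) | −0.2326 | −0.1827 | −0.1482 |
| Required n, P = 19 | 817 | 1,040 | 1,282 |
| 934 minus required n | +117 | −106 | −348 |
| Expected S at n = 934 | 0.911 | 0.890 | 0.868 |
| Largest P for S = 0.9 at 934 | 21 | 17 | 13 |

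Expected S is the value that solves the shrinkage formula at n = 934. The largest P is 934 × 0.1 × |ln(1 − R²/0.9)|, rounded down from 21.7, 17.1 and 13.8.

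**Other criteria.** Optimism in Nagelkerke R² of at most 0.05 requires about 449, 573 and 708. Estimating overall risk within ±0.05 requires about 380, 219 and 148. Shrinkage is the binding criterion throughout.

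**Sensitivity.**

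- With the printed rates in place of exact counts, the minima are 826, 1,041 and 1,283.
- Counting the three-category depression/anxiety item as two parameters (P = 18) gives 986 for >180 days and 1,215 for WAA/DP, both still above 934.
- With only the 13 parameters of Table 2 and no curvature terms, the minima are 712 and 877, and 934 suffices.
- For 934 to suffice at P = 19, Nagelkerke R² would have to be about 27.6% for >180 days and 33.4% for WAA/DP.

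**End-point 1.** 416/934 = 0.445, whereas 0.403 × 934 is about 376 events. The stated 368 events follow 0.445 (826 × 416/934 = 367.9), as does the figure of about 19.4 events per parameter (368/19). At 0.403 the events would be 826 × 0.403 = 333. The event figures therefore use one rate and the R² appears to use the other.

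**The case against.** The strongest reply is that little depends on the error. The sample is already fixed, so no recruitment decision rests on it. The 25% is only an assumption, and 0.9 is a planning target that triggers no rule. For >180 days the miss is 0.890 against 0.90, and a Nagelkerke R² of 27.6% would close it. The Model performance section plans 500 bootstrap samples that repeat all modelling steps, a shrinkage factor applied to the coefficients and a re-estimated intercept, and external validation follows. Overfitting will therefore be measured and corrected. Finally, the SAP presents 19 parameters as what the chosen factors require, and does not show that 19 was derived from 826.

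Much of this stands as a limit on the consequences. End-point 2 is marginal and end-point 3 is the material case. Neither model becomes infeasible. But bootstrap correction after fitting does not make an advance statement of adequacy true, and minimal shrinkage is what that statement promises. Nor can the conclusion be rescued by a higher R², because the plan states 25% and gives no grounds for 33%. On the number of parameters, the SAP itself says factor selection was restricted by the sample-size calculation, so the two are linked even if 19 was partly an input.

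**Conclusion.** The concern holds. Under the plan's own assumptions (Nagelkerke R² 25%, 19 parameters, shrinkage 0.9), the minima are 817, 1,040 and 1,282, not 826 three times. The sample of 934 meets the first and falls short of the second by 106 (11% of 934) and the third by 348 (37% of 934). The claim of adequacy is wrong for two of three models, slightly for >180 days and materially for WAA/DP. The result does not depend on rounding or on how the depression/anxiety item is counted. It would change only with a higher assumed R² or fewer parameters. The mismatch between 0.403 and 416/934 is a separate error and leaves the conclusion for end-point 1 intact, since both 817 and 826 lie below 934.

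**What to change.** In Sample size, Development:

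1. Replace the single 0.185 with Cox-Snell values of 0.187, 0.150 and 0.124, and state the event rate behind each.
2. Restate the minima as 817, 1,040 and 1,282, with the matching event counts and events per parameter. Note that exact counts and unrounded R² were used, because the three-decimal values give slightly different results (about 1,043 for >180 days).
3. Reconcile 0.403 with 416 of 934. If 416 is right, the rate is 0.445; if 0.403 is right, the count, the events and the events per parameter all change.
4. Restrict the adequacy sentence to end-point 1.
5. For end-points 2 and 3, choose one course before modelling. Either keep 19 parameters and state expected shrinkage of about 0.89 and 0.87, relying on the planned bootstrap correction, or cap the models at 17 and 13 parameters.

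The minimum repair is a re-run of the calculator and revised wording, with no extra participants. The stated figures become less favourable. The cap is optional and has a price: the >180-day model loses some of its allowance for curvature, and the WAA/DP model loses all of it, which would have to be squared with the planned check for non-linearity. In either case the exploratory-factor section should acknowledge that, with 19 parameters already in use, there is no room for further predictors in models 2 and 3 at the 0.9 target.
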